### **7.3 Laboratory Test Abnormalities**

All laboratory test results captured as part of the study should be recorded following institutional procedures. Test results that constitute SAEs should be documented and reported as such.

The following laboratory abnormalities should be documented and reported appropriately:

- any laboratory test result that is clinically significant or meets the definition of an SAE
- any laboratory abnormality that required the subject to have study drug discontinued or interrupted
- any laboratory abnormality that required the subject to receive specific corrective therapy

### **7.4 Overdose**

An overdose is defined as the accidental or intentional administration of any dose of a product that is considered both excessive and medically important. All occurrences of overdose must be reported as an SAE.

### **7.5 Pregnancy**

If, following initiation of the investigational product, it is subsequently discovered that a study subject is pregnant or may have been pregnant at the time of investigational product exposure, including during at least 6 half lives after product administration, the investigational product will be permanently discontinued in an appropriate manner (eg, dose tapering if necessary for subject safety).

Protocol-required procedures for study discontinuation and follow-up must be performed on the subject unless contraindicated by pregnancy (eg, x-ray studies). Other appropriate pregnancy follow-up procedures should be considered if indicated.

The investigator must immediately notify the BMS (or designee) Medical Monitor of this event and complete and forward a Pregnancy Surveillance Form to BMS (or designee) within 24 hours and in accordance with SAE reporting procedures described in Section 7.2.1

Follow-up information regarding the course of the pregnancy, including perinatal and neonatal outcome and, where applicable, offspring information must be reported on the Pregnancy Surveillance Form.

Any pregnancy that occurs in a female partner of a male study participant will be reported to BMS. Information on this pregnancy will be collected on a Pregnancy Surveillance Form.

**7.6 Potential Drug-Induced Liver Injury (DILI):** Wherever possible, timely confirmation of initial liver-related laboratory abnormalities should occur prior to the reporting of a potential DILI event. All occurrences of potential DILIs, meeting the defined criteria, must be reported as SAEs (see Section 7.2.1 for reporting details).

Potential drug induced liver injury is defined as

1. AT (ALT or AST) elevation > 3 times upper limit of normal (ULN)  
AND
2. Total bilirubin > 2 times ULN, without initial findings of cholestasis (elevated serum alkaline phosphatase),  
AND
3. No other immediately apparent and/or possible causes of AT elevation and hyperbilirubinemia, including, but not limited to, viral hepatitis, pre-existing chronic or acute liver disease, or the administration of other drug(s) known to be hepatotoxic.

## 7.7 Other Safety Considerations

Any significant worsening noted during interim or final physical examinations, electrocardiograms, x-rays, and any other potential safety assessments, whether or not these procedures are required by the protocol, should also be recorded as a nonserious or serious AE, as appropriate, and reported accordingly.

## 8 Data Monitoring Committee

A data monitoring committee will be formed with four members and a minimum of two rheumatologists who are expert lupus physicians. SAE reports will be sent to the DSMB members along with IRB/BMS submission. Routine AEs will be reported on a quarterly basis. A full set of laboratory reports will also be sent to the DSMB. Flare data will also be reported, whether or not any given flare was attributed to adverse event or study medication. Safety reports will be reviewed quarterly or as deemed appropriate, based on SAE reports. The DSMB can be unblinded at request but will not be routinely unblinded to data, nor will efficacy data be reported during the trial, since the small number of patients does not justify a specific risk/benefit assessment during the course of the trial. The DSMB will be

provided with the safety and flare data from the previous abatacept lupus trials to use as a comparison to what they are reviewing. Unexpected flare or AE reports could then trigger unblinding

of the DSMB. The DSMB may request consultation by an infectious disease or other specialist to help with their assessment of the data.

## 9. Statistical Considerations

**Enrollment is expected to include at least 70 screened and 60 randomized subjects** subjects have either reached a six month endpoint and/or been defined as a permanent non-responder for off protocol treatment or by dropping out of the protocol.

**The primary endpoint is the proportion of placebo vs treatment subjects who meet the primary endpoint of BICLA response using Chi Square analysis at month 6 as determined by an intent to treat analysis**

Subjects who drop out prematurely for any reason or are treated with off protocol medications or cross over to open label for lack of response at Month 3-6 are considered non responders at month 6.

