Statistics:	
Primary Clinical Endpoint: proportion of patients on abatacept vs placebo who meet BICLA criteria at month 6 compared to baseline by Ch sq or Fishers Exact Test. Powering of the Study Based on the Primary Endpoint: Powering assumptions assume response rates ranging from 35-50%. based on data from patients with lupus arthritis in the Phase II abatacept study, where physicians rated 40% of the patients treated with abatacept as having “no flare.” Using the BICLA, response rates in the epratuzumab EMBLEM trial was also about 40% at optimal dosing, therefore this range seems applicable. Data from the BOLD study confirm that there should be a near zero (2.4%) percent response by BICLA at six months in the placebo group in a study with background IS withdrawal. Therefore our assumption of at least 5% response in the placebo group in an identical trial design is reasonable and with range of 40-50% response in the treatment group power > 0.8 to detect a difference. Exploratory Analysis of Primary Endpoint: To address potential confounders in a small study a propensity score will be applied to simplify multiple variables into one variable.
 
Secondary Clinical Endpoints: BICLA and SRI at each month. Mean SLEDAI, BILAG, CLASI, PGA, DIAL and PRO by paired T test. Main Biologic Endpoint: Patients who do or do not exhibit proposed relative differences in the ratio of IL6/IL23/IL17 to Foxp3/TGF<math>\beta</math> (suggesting T Cell signaling imbalance) or aberrant ErK phosphorylation (indicating abnormal signaling through B Cell receptor) at baseline will be compared for proportion of responders in treatment vs placebo group. Patients identified at baseline with high TH17 signal or ErK phosphorylation with <math>\geq</math> 50% change towards healthy mean (+2SD) after treatment will be compared separately for response rates. These endpoints will be described in terms of confidence intervals based on the primary clinical endpoint. Analysis of Secondary and Exploratory Biologic Endpoints will include mean (or median) change in cytokine, immunoglobulin and gene expression levels explored based on known patterns of overexpression in SLE. Bucketing of baseline profiles might be used to develop propensity scores suitable for a simplified refinement of the primary biologic endpoint by combining variables that might either increase or decrease the likelihood of response. Given the complex array of data we are likely to generate, principal component analysis can be applied to these exploratory studies to identify directions (principal components) along which the variation of the data is maximal.

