## 1.6 STUDY RATIONALE

This double blind placebo controlled study will randomize lupus patients with active arthritis to abatacept or placebo for a six month trial to determine which group has a greater response rate as measured by the primary endpoint of BICLA (BILAG based Combined Lupus Assessment ) (BILAG=British Isles Lupus Assessment Group index). The dose of 125 mg administered subcutaneously weekly has been validated in an RA population and was chosen for this study in SLE on the basis of the assumption that it will be equal in efficacy to intravenous infusion without adversely affecting the safety profile. This current small study is not designed to test that assumption, but on the basis of RA data it seems reasonably likely that any efficacy signal from abatacept will be detectable through this route of administration in SLE. Subcutaneous dosing is a more practical clinical approach in the management of patients overall, is much easier for the patients, and will lessen the costs of an investigator initiated study while being unlikely to negatively affect either patient safety or the information that can be obtained.

The rationale for this study design, which is based on exploratory analysis of previous abatacept and other lupus studies, is to provide a more discriminatory protocol and a more robust endpoint than was available in prior trials for lupus. A further rationale is to provide proof of concept for the general feasibility of smaller pre-Phase III trials in SLE with greater potential effect size than has been possible in the past and ability to make confident go/no go decisions for Phase III development after less investment of time, patient risk, and expense than is usual in Classic Phase II designs.

Indeed this project is specifically powered (based on data about placebo group response rates from our BOLD study, a prior, similar study) to support a rational decision about further development of abatacept for SLE.

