### 9.1 Sample Size Determination

**Sample Size** Based on data from the BOLD study confirming the low response rates in a placebo group at 6 months in a study design identical to the structure of this protocol (1/41 patients or 2.4% met the BICLA response at 6 months in that study) and based on the assumption that the response rate to abatacept using this design and these endpoints would be at least equivalent to what was found in the Phase II Epratuzumab or Phase III BLISS studies (roughly 40-50% response). The sample size was optimized at 60 patients in a 1:1 randomization scheme with alpha = 0.5 and desired power 0.8.

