### 9.2 Populations for Analyses

**The subject population** As further detailed in the inclusion and exclusion criteria will consist of consecutive consenting lupus patients between ages 18 and 70 who have active polyarticular arthritis characterized by 3 or more tender and 3 or more swollen joints at the screening visit meeting the BILAG 2004 criteria for  $\geq$  B disease (+/- additional evidence of disease activity in other organs).

**The clinical justification** is based on the combination of unmet need in treating a significant, potentially disabling illness, while ensuring a healthy enough population to justify the risks of studying a biologic treatment vs placebo.

**Power Analysis:** Chi Sq or the Fisher's exact test will be used for analysis. The table below has been powered on the assumption that the placebo group will have a result similar to (or even a bit more responsive than) that found in the BOLD study (which was the test prototype for this protocol to determine the safety and feasibility of the statistical assumptions for the placebo study). Data from the BOLD study confirm that there should be a near zero (2.4%) percent response by BICLA at six months in the placebo group in a study with background IS withdrawal. Therefore our assumption of at least 5% response in the placebo group in an identical trial design is reasonable. The second assumption is that the treatment group will have a response rate somewhere between those found in the epratuzumab (by BICLA) and BLISS phase II/III (by SRI) biologic studies e.g. a predicted response rate between 35 and 50%. The most important basis for this assumption, however are the data from patients with lupus arthritis in the Phase II abatacept study, where physicians rated 40% of

the patients treated with abatacept as having “no flare” after baseline. Therefore this expected range by BICLA seems reasonable. (please see power analysis table below which is based on powering the primary endpoint at a range of expected response rates in treatment and placebo groups with a sample size of 60 patients, alpha=0.05).

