#### **Power of 60 patient study if alpha=0.05 with response rates:**

	Rate 1	Rate 2	Rate 3	Rate 4	Rate 5	Rate 6	Rate 7
abatacept	60%	55%	50%	45%	40%	35%	35%
placebo	20%	15%	10%	10%	5%	5%	3%
power	0.84	0.86	0.89	0.80	0.86	0.77	0.84

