#### **9.4.3 Efficacy Analysis**

**Primary Endpoint:** The primary analysis upon which this study is powered will be a two by two analysis of response rates to BICLA endpoint in treatment vs placebo group.

**Exploratory Analysis of Primary Endpoint:** To address potential confounders in a small study a propensity score will be applied to simplify multiple variables into one variable.

**Analysis of Secondary Clinical Endpoints:** include the BICLA and SRI response performed at each month using a Chi Square approach as well as mean SLEDAI, BILAG, CLASI, PGA, DIAL and PRO by paired T test comparing baseline to endpoint (EOS or each month) in placebo patients and separately in abatacept treated patients.

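### The primary test is stated inconsistently, with no rule for choosing; if chi-square is uncorrected, the two permitted tests can give opposite verdicts on the same data

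*Combined protocol and SAP*

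**What the plan says.** Four places describe the primary comparison of month 6 BICLA response.

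- Section 9, opening text: chi-square only, "using Chi Square analysis at month 6 as determined by an intent to treat analysis".
- Synopsis, Statistics: either test, "compared to baseline by Ch sq or Fishers Exact Test".
- Section 9.2, Power Analysis paragraph: either test again, "Chi Sq or the Fisher's exact test will be used for analysis".
- Section 9.4.3, primary endpoint: "two by two analysis of response rates to BICLA endpoint in treatment vs placebo group", with no test named. Chi-square does appear later in that section, but for BICLA and SRI at each month, which are secondary endpoints.

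The significance level also varies. Section 9.1 gives "60 patients in a 1:1 randomization scheme with alpha = 0.5 and desired power 0.8", while the table after Section 9.2 is headed "Power of 60 patient study if alpha=0.05 with response rates". The table does not say which test its powers are for. Section 1.6 presents the trial as one with the "ability to make confident go/no go decisions for Phase III development".

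**The concern.** No section says when Fisher replaces chi-square, whether chi-square carries a continuity correction, or whether the test is one- or two-sided. The expected placebo response is very low (1 of 41 in the BOLD study, 5% assumed here), and small cell counts are where these tests diverge. For a result near the threshold, the primary verdict could rest on a choice that the plan leaves open until after the data are seen, and nobody could then show that the choice was independent of the result. What is at stake is how a borderline outcome is read in a trial meant to inform a development decision.

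**Working it through.** **Inputs.** 60 patients randomised 1:1 (Section 9.1), taken as exactly 30 per arm. Alpha 0.05 (Section 9.2 and the power table). Two-sided is an assumption, because the documents do not say. Response rates are those of the power table. Dropouts count as non-responders, so they stay in the denominator.

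**1. The plan's own power table.** Two-sided normal approximation with continuity correction, where p̄ is the mean of the two rates:

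power = Φ{[p1 − p2 − 1/n − 1.96·√(2p̄(1−p̄)/n)] / √[(p1(1−p1) + p2(1−p2))/n]}

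For 40% v 5%: numerator 0.350 − 0.0333 − 1.96 × 0.1078 = 0.1053; denominator 0.0979; ratio 1.076; power 0.859, against 0.86 stated.

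Exact power comes from enumerating all 31 × 31 = 961 tables, weighting each by its binomial probability and summing those with p ≤ 0.05. The split column is the probability that uncorrected chi-square is significant and Fisher is not.

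| Abatacept / placebo (%) | Stated | Corrected formula | Exact Fisher | Exact uncorrected chi-square | Split |
|---|---|---|---|---|---|
| 60 / 20 | 0.84 | 0.848 | 0.851 | 0.905 | 0.054 |
| 55 / 15 | 0.86 | 0.869 | 0.876 | 0.922 | 0.046 |
| 50 / 10 | 0.89 | 0.897 | 0.914 | 0.949 | 0.035 |
| 45 / 10 | 0.80 | 0.804 | 0.830 | 0.891 | 0.061 |
| 40 / 5 | 0.86 | 0.859 | 0.893 | 0.943 | 0.050 |
| 35 / 5 | 0.77 | 0.749 | 0.788 | 0.880 | 0.092 |
| 35 / 3 | 0.84 | 0.830 | 0.875 | 0.946 | 0.072 |

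The stated values are within about 0.01 of the corrected formula in six columns and 0.02 away at 35/5. They lie 0.011 to 0.035 below exact Fisher power and 0.059 to 0.11 below exact uncorrected chi-square power.

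**2. Same data, different verdicts.** With a and b responders among 30 per arm, uncorrected X² = 60·(a(30−b) − b(30−a))² / (30·30·(a+b)·(60−a−b)).

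- 5 v 0: 60 × 150² / (900 × 5 × 55) = 5.45, p = 0.020. Fisher: 2 × C(30,5)/C(60,5) = 2 × 142,506/5,461,512 = 0.052. Yates: 60 × (150 − 30)² / 247,500 = 3.49, p = 0.062.
- 8 v 2: 60 × 180² / (900 × 10 × 50) = 4.32, p = 0.038. Fisher 0.080, Yates 0.083.
- 10 v 3: 60 × 210² / (900 × 13 × 47) = 4.81, p = 0.028. Fisher 0.057, Yates 0.060.

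With 0, 1 or 2 placebo responders, significance needs 4, 6 or 8 abatacept responders by uncorrected chi-square, and 6, 8 or 9 by Fisher.

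**3. Direction and extent.** Of the 961 tables, 54 split (27 of them favouring abatacept). In all 54, uncorrected chi-square is significant and Fisher is not; none goes the other way. Yates-corrected chi-square and Fisher give the same verdict on all 961.

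**4. Type I error.** Because the split runs one way, always reporting the smaller p-value is the same as always using uncorrected chi-square. Maximum size over a common response rate is 0.055 for uncorrected chi-square and 0.027 for Fisher.

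**5. The 0.5 in Section 9.1.** At alpha 0.5, exact power would be 0.985 to 0.999 in every column under either test, so the table was not computed at that level. The evident intent is 0.05.

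**The case against.** The best defence is that the plan does point to a test. Chi-square is the only one named in Section 9 and for monthly BICLA in Section 9.4.3, and many readers would take the alternative wording as the usual convention of using Fisher when expected counts are small. If a continuity-corrected chi-square was meant, there is no conflict on any table at 30 per arm, and the power table comes close to such a calculation at the stated size. At the planned rates, at least about 91% of outcomes get the same verdict either way. Section 9.4.4 also allows development to continue on a large effect without significance.

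All of that limits the consequence, but none of it closes the gap. The convention is not written down, the correction is not stated, and the power table does not name its test.

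Three stronger readings are tempting and not supported.

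- A reader might infer that the trial is underpowered. The synopsis claims power above 0.8 "with range of 40-50% response in the treatment group power"; at 40% v 5% Fisher gives 0.893 and uncorrected chi-square 0.943, and power rises with the abatacept rate.
- A reader might infer serious false-positive inflation. The ceiling is 0.055.
- A reader might infer a one-sided test from the directional hypothesis in Section 1.5. No section mentions one, and Section 1.6 asks without direction which arm responds more.

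**Conclusion.** The inconsistency is real and should be fixed. Its size is a 3.5% to 9.2% chance, across the plan's own scenarios, that the primary result is positive under one permitted test and negative under the other. That figure rests on 30 per arm, two-sided 0.05 and an uncorrected chi-square; with Yates' correction the chance is zero. The harm is an undetermined verdict near the threshold, not a loss of power or a material loss of type I control. The alpha of 0.5 in Section 9.1 is an apparent misprint, but it stands where the decision threshold is stated.

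**What to change.** Before unblinding:

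1. Use one sentence in the synopsis, Section 9, Section 9.2 and Section 9.4.3, and remove the alternative. For example: *Month 6 BICLA response will be compared between arms by [Fisher's exact test / Pearson chi-square without continuity correction], two-sided, alpha 0.05.* Either test already in the plan cures the defect.
2. Correct alpha in Section 9.1 to 0.05.
3. State in the power table which test and method its values are for. The present values are slightly conservative for Fisher. If the row is restated as exact power at 30 per arm, in the table's column order, it reads:
   - Fisher: 0.85, 0.88, 0.91, 0.83, 0.89, 0.79, 0.87
   - Uncorrected chi-square: 0.90, 0.92, 0.95, 0.89, 0.94, 0.88, 0.95

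   (Fisher at 35/3 is 0.8746 and chi-square at 60/20 is 0.9046 before rounding.)

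The cost is wording and one table; patients, visits and sample size do not change. The choice is a trade-off. Fisher gives up 0.035 to 0.092 in power against uncorrected chi-square, while uncorrected chi-square can slightly exceed its nominal size (0.055).

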### 9.1 Sample Size Determination

**Sample Size** Based on data from the BOLD study confirming the low response rates in a placebo group at 6 months in a study design identical to the structure of this protocol (1/41 patients or 2.4% met the BICLA response at 6 months in that study) and based on the assumption that the response rate to abatacept using this design and these endpoints would be at least equivalent to what was found in the Phase II Epratuzumab or Phase III BLISS studies (roughly 40-50% response). The sample size was optimized at 60 patients in a 1:1 randomization scheme with alpha = 0.5 and desired power 0.8.

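### Section 9.1 gives alpha = 0.5 for the 60-patient sample size; Section 9.2 and the power table give 0.05, and 0.5 cannot produce the printed powers

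*Combined protocol and SAP*

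**What the plan says.** Three places describe the same 60-patient, 1:1 design and give a significance level:

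- Section 9.1, Sample Size Determination: "The sample size was optimized at 60 patients in a 1:1 randomization scheme with alpha = 0.5 and desired power 0.8".
- Section 9.2, in the power analysis paragraph, introducing the table for the primary endpoint: "range of expected response rates in treatment and placebo groups with a sample size of 60 patients, alpha=0.05".
- The heading of the power table: "Power of 60 patient study if alpha=0.05 with response rates".

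The sentences that define the primary analysis give no level. The opening of Section 9 asks for a comparison of subjects who "meet the primary endpoint of BICLA response using Chi Square analysis at month 6 as determined by an intent to treat analysis", and Section 9.4.3 calls it "a two by two analysis of response rates to BICLA endpoint in treatment vs placebo group". The statistics part of the synopsis also gives no alpha. The synopsis and Section 9.2 allow either chi-square or Fisher's exact test. The document does not say whether the level is one- or two-sided, or whether a continuity correction was used.

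**The concern.** The sample-size section is where a reader looks for the type I error rate, and it prints a value ten times the one given in the next section. Read literally, it would allow a false-positive rate of one in two. The primary-analysis sentences and the synopsis cannot correct it because they state no level.

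The level matters to how the result will be used. Section 1.6 says the trial is powered to inform a decision on developing abatacept further in SLE, and Section 9.4.4 discusses the case where the primary endpoint does not reach significance. Both need a correctly stated threshold.

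**Working it through.** **Inputs.** N = 60 at 1:1, so n = 30 per arm (Section 9.1). The seven pairs of response rates and printed powers come from the power table. Target power is 0.8 (Section 9.1). Alpha is 0.5 (Section 9.1) or 0.05 (Section 9.2 and table heading). Two-sided testing and the continuity correction are my assumptions.

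**Formula.** Pooled-variance normal approximation with continuity correction, where p̄ = (p1 + p2)/2:

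power = Φ{ [ |p1 − p2| − 1/n − z·SE0 ] / SE1 }, with SE0 = √(2p̄(1 − p̄)/n) and SE1 = √([p1(1 − p1) + p2(1 − p2)]/n).

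**Worked column, 45% versus 10%.** p̄ = 0.275, SE0 = 0.1153, SE1 = 0.1061, and 0.35 − 1/30 = 0.3167.

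- Alpha 0.05, z = 1.960: (0.3167 − 0.2260)/0.1061 = 0.855, power 0.804. The table prints 0.80.
- Alpha 0.5, z = 0.674: (0.3167 − 0.0778)/0.1061 = 2.252, power 0.988.

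**All columns, 30 per arm, two-sided.**

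| Abatacept / placebo | Printed | Corrected, 0.05 | Fisher exact, 0.05 | Uncorrected, 0.05 | Corrected, 0.5 |
|---|---|---|---|---|---|
| 60 / 20% | 0.84 | 0.848 | 0.851 | 0.906 | 0.993 |
| 55 / 15% | 0.86 | 0.869 | 0.876 | 0.922 | 0.994 |
| 50 / 10% | 0.89 | 0.897 | 0.914 | 0.943 | 0.996 |
| 45 / 10% | 0.80 | 0.804 | 0.830 | 0.879 | 0.988 |
| 40 / 5% | 0.86 | 0.859 | 0.893 | 0.922 | 0.994 |
| 35 / 5% | 0.77 | 0.749 | 0.788 | 0.846 | 0.980 |
| 35 / 3% | 0.84 | 0.830 | 0.875 | 0.905 | 0.991 |

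At 0.05 the largest gap from print is 2.1 points with the correction, 3.5 points with Fisher and 7.9 points without correction. At 0.5, Fisher gives 0.985 to 0.996, and the uncorrected formula is higher than the corrected one in every column. No method tried at 0.5 comes near the printed range.

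**Sample size for 45% versus 10% at power 0.80.** Uncorrected, n0 = [z·√(2p̄(1 − p̄)) + 0.842·√(p1(1 − p1) + p2(1 − p2))]² / (p1 − p2)². Corrected, n = (n0/4)·[1 + √(1 + 4/(n0·|p1 − p2|))]².

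- Alpha 0.05: n0 = 24.3, n = 29.8, so 30 per arm and 60 in total, which is the planned size.
- Alpha 0.5: n0 = 6.8, n = 11.9, so 12 per arm and 24 in total.

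**Is the fit at 0.05 unique?** No. Three other settings lie closer to the printed powers than the corrected two-sided 0.05 calculation with 30 per arm (2.1 points):

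- uncorrected, two-sided 0.025, 30 per arm: largest gap 0.7 points;
- uncorrected, two-sided 0.05, 25 per arm: largest gap 1.1 points;
- corrected, one-sided 0.05, 25 per arm: largest gap 1.2 points.

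The document describes none of these three, but it does not mention a continuity correction either.

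**The case against.** The strongest reply is that nobody would be misled for long. The value 0.05 appears twice straight after Section 9.1 and is tied to the primary endpoint. Section 9.4.3 refers to the analysis on which the study is powered, which points back to that value. This stands, and it is why the point is only an erratum. It does not make 0.5 correct.

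Three stronger readings are tempting, and the documents do not support them.

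- A reader might infer that the trial was sized, or will be tested, at 0.5. The printed powers and N = 60 rule out the first. Nothing outside Section 9.1 suggests the second.
- A reader might infer that the table proves a two-sided level of 0.05. It does not. That match needs a correction the document never mentions, and other combinations of level, sidedness and arm size match more closely. The table excludes 0.5; the choice of 0.05 rests on the text of Section 9.2 and the table heading.
- A reader might object to the phrase in "Therefore our assumption of at least 5% response in the placebo group in an identical trial design is reasonable", since power falls as placebo response rises. In context, 5% is a cautious planning value above the 2.4% seen in BOLD: Section 9.2 expects a placebo result "similar to (or even a bit more responsive than) that found in the BOLD study". The synopsis claim of power above 0.8 holds at 5% placebo response, and the table already covers placebo rates from 3% to 20%. That is a preference about wording, not an error.

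**Conclusion.** Wrong as written; minor. Section 9.1 contradicts Section 9.2 and the power table by a factor of ten on the significance level. At 0.5 the powers would be 11 to 21 points above print with the continuity-corrected formula (for example 0.996 against 0.89, and 0.980 against 0.77). A 60-patient design would also be 2.5 times the 24 patients needed for 45% versus 10%.

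The contradiction rests on the text alone. Rejecting 0.5 assumes 30 per arm and holds for the corrected, uncorrected and Fisher calculations. Sidedness and the method behind the table remain unknown: two-sided is the usual convention, but only the authors can confirm it.

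**What to change.** In Section 9.1, change the level from 0.5 to 0.05.

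The authors should also confirm and state two things, once, beside the primary test in Section 9.4.3 or in Section 9.1:

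- whether 0.05 is one- or two-sided;
- which test, and which continuity correction if any, produced the power table. If the level is two-sided and the test is uncorrected chi-square, a reader who recalculates the table will get values 5 to 8 points higher, so the method needs naming.

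The cost is one digit and one sentence. The sample size, the primary test and trial conduct do not change.
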